6.3 Efficacy

6.3.1 Efficacy variable

6.3.1.1 Efficacy laboratory variable

The laboratory parameters that will be measured to assess efficacy are displayed in [Table 7](#) by visit.

Table 7 Efficacy laboratory variable

Visit	1	2	3	4	5	6	7	8	9	10	11	12	13	14
Week	-12	-10	-6	-4	-1	0	1	2	4	6	8	10	12	16
HbA1c	X				X	X			X	X	X	X	X	X
FPG	X	X	X	X	X	X	X	X	X	X	X	X	X	X
Total-C						X							X	
LDL-C						X							X	
HDL-C						X							X	
TG						X							X	
FFA						X							X	
Fasting Insulin	X					X				X			X	
C-peptide	X					X				X			X	

The laboratory parameters will be analyzed by a central laboratory. The result of HbA1c from Visit 6 (Week 0) and onwards will not be reported to subjects, the investigators and the sponsor. The results of FPG from baseline and onwards will not be reported to subjects.

6.3.1.2 Oral Glucose Tolerance Test (OGTT) Procedure

At Week 0, OGTT is performed in only those subjects whose FPG is less than 180 mg/dL at Week -1. At Week 12, OGTT is not performed in subjects who did not perform OGTT at Week 0, subjects who did not complete period C or subjects whose FPG \geq 180 mg/dL at Week 10.

- At Week 0 (randomization), study medication is given as soon as possible AFTER OGTT is complete
- At Week 12 (or at end of study visit), the study medication is given 1 hour BEFORE administration of 75 g oral glucose solution.
- Instruct subject to empty bladder after obtaining urine sample.
- Insert saline lock, if appropriate.

- Draw Time 0 blood sample for glucose, insulin, C-peptide
- Immediately after Time 0 blood sample is drawn above: Administer 75 g of oral glucose.
- Draw blood specimens for post prandial glucose, insulin and C-peptide at 60, 90, 120, 180 and 240 minutes.
- Collect all urine voided after emptying of bladder up to and including attempted void after removal of saline lock for the measurement of total volume urinary glucose, creatinine, and sodium concentration.
- Remove saline lock.

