2.3 Tertiary Objectives

Tertiary Objectives	Tertiary Outcome variable(s)
1. To assess the differences of the change from baseline for each dose of dapagliflozin vs placebo after 12 weeks of oral administration of double-blind treatment for the following parameters:	1. (a) Change from baseline in AUC from 0 to 180 minutes for postprandial glucose, insulin, and C-peptide response to an OGTT at Week 12.
(a) Area under the curve (AUC) from 0 to 180 minutes for postprandial glucose, insulin, and C-peptide response to an oral glucose tolerance test (OGTT)	(b) Change from baseline in fasting plasma insulin at Week 12.
(b) Fasting plasma insulin	(c) Change from baseline in fasting C-peptide at Week 12.
(c) Fasting plasma C-peptide	(d) Change from baseline in beta-cell function (as measured by HOMA2) at Week 12.
(d) Beta-cell function (as measured by Homeostasis Model Assessment version 2 (HOMA2))	(e) Change from baseline in insulin resistance (as measured by HOMA2) at Week 12.
(e) Insulin resistance index (as measured by HOMA2)	

Tertiary Objectives	Tertiary Outcome variable(s)
2. To assess each dose of dapagliflozin and placebo after 12 weeks of oral administration of double-blind treatment for the following:	2.
(a) Changes from baseline in glucose, C-peptide, and insulin concentrations at 0, 30, 60, 120 and 180 minutes during an OGTT	(a) Change from baseline in glucose, C-peptide and insulin concentrations at 0, 30, 60, 120, and 180 minutes postprandial values during an OGTT at Week 12.
(b) Change from baseline in the respective excretion profiles for plasma glucose, C-peptide, and insulin concentrations (defined as the difference between 0 and 30, 60, 120 and 180 minute postprandial values) during an OGTT	(b) Change from baseline in the respective excretion profiles for plasma glucose, C-peptide and insulin concentrations (defined as the difference between 0 and the 30, 60, 120, and 180 minutes postprandial values) during an OGTT at Week 12.
(c) Change from baseline in the insulin sensitivity and beta-cell function derived from measurements of insulin, C-peptide, and glucose during the OGTT	(c) Change from baseline in the insulin sensitivity and beta-cell function derived from measurements of insulin, C-peptide and glucose during the OGTT at Week 12.
(d) Change from baseline in body mass index (BMI), waist circumference, and total body weight	(d) Change from baseline in BMI, waist circumference, and total body weight at Week 12.

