- c All randomized subjects not completing the treatment period should have Visit 13 procedures done as soon as possible but at the latest within 7 days after discontinuation of investigational products, and subsequently enter the 4-week follow-up period.
- d Glucose meter is provided to subjects and they check their blood glucose values if they have symptoms of hypoglycemia.
- e Call Registration Center to enroll subjects when informed consent is obtained at Visit 1, to randomize subjects at Visit 6, and when subject completes Period C or early discontinue Period C.
- f Subjects treated with anti-diabetic medication up to enrolment should have HbA1c ≤ 8% at Visit 1 to enter Period A, and the other type of subjects will enter Period B if HbA1c ≥ 7% but ≤ 10% at visit 1. All subjects should have HbA1c ≥ 7% but ≤ 10% at visit 5 to be randomized.
- g Subjects treated with anti-diabetic medication up to enrolment will be withdrawn if FPG > 240 mg/dL.
- h At Visit 6, OGTT is performed if FPG is <180 mg/dL at visit 5. At Visit 13, OGTT is not performed in subjects who did not perform OGTT at Visit 6, subjects who did not complete period C or subjects whose FPG is ≥ 180 mg/dL at Visit 12. At Visit 13, blood samples are drawn 60, 90, 120, 180 and 240 minutes after administration of 75 g oral glucose solution.
- i Plasma samples for analysis of dapagliflozin are obtained before administration of dapagliflozin at Visit 7, 10 and 12. At Visit 13 plasma samples are obtained at 60, 90, 120, 180 and 240 minutes after administration of dapagliflozin. If the subjects perform OGTT at Visit 13, plasma samples are obtained simultaneously with OGTT blood samples.
- j 24 hour urine collection is done in subjects who give consent. 24 hour urine is collected from the morning of the previous day to the visit up to the morning of the visit. 24 hour urine collection is allowed to be done on a separate day of the study visit if collected within 7 days before the visit. Subjects do not need to perform 24 hour urine collection at visit 6 if they do not meet HbA1c ≥ 7% but ≤ 10% at Visit 5. At Visit 13(Week 12), 24 hour urine is not performed in subjects who did not complete Period C

Clinical Study Protocol
Drug Substance Dapagliflozin
Study Code D1692C00005
Edition Number 1
Date

k Includes anti-HAV (IgM, IgG), HBsAg, and anti-HCV, and anti-HBc

Table 2 Visit design and time windows

Visit ID	Visit description	Visit window
Visit 1	Enrolment (Screening) ^a	-12 weeks

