6.7 Pharmacodynamics – Not Applicable

6.8 Pharmacogenetics – Not Applicable

6.9 Health economics – Not Applicable

7. BIOLOGICAL SAMPLING PROCEDURES

7.1 Volume of blood

The total volume of blood that will be drawn from each subject at maximum in this study is as follows:

Table 8 Volume of blood to be drawn from each subject

Visit	1	2	3	4	5	6	7	8	9	10	11	12	13	14	Total
Assessment															
Haematology	2			2		2	2	2	2	2	2	2	2	2	22
Serum blood sampling ^a	10			5		13	5	5	5	10	5	5	13	10	86
HbA1c	2				2	2			2	2	2	2	2	2	18
FPG	2	2 ^b	2 ^b	2	2	2	2	2	2	2	2	2	2	2	28
Markers of bone metabolism ^c						10					10		10	10	40
PT, APTT	1.8														1.8

Table 8 Volume of blood to be drawn from each subject

Visit	1	2	3	4	5	6	7	8	9	10	11	12	13	14	Total
Assessment															
OGTT ^d						10							10		20
PK sample ^e							3			3		3	15		24
Total	17.8	2	2	9	4	39	12	9	11	19	21	14	54	26	239.8

- ^a Serum blood sampling for Clinical chemistry, Fasting Insulin, C-peptide, Fasting serum lipids (TC, LDL-C, HDL-C, TG, and FFA), Hepatitis Screen Panel (anti-HAV (IgM, IgG), HBsAg, anti-HCV, and anti-HBc), Thyroid Stimulating Hormone, Cystatine C. Blood volume depends on the assessment for each visit.
- ^b If subject treated with anti-diabetic medication up to enrolment.
- ^c Parathyroid hormone, osteocalcin, 25-vitamin D, C-terminal cross-linking telopeptides of type I collagen (CTX), Bone-specific alkaline phosphates and Procollagen type-1 N-terminal propeptide (PINP)
- ^d Visit 13, OGTT is not performed in subjects who did not perform OGTT at Visit 6, subjects who did not complete period C or subjects whose FPG is ≥ 180 mg/dL at Visit 12. At Visit 13, blood samples are drawn 60, 90, 120, 180 and 240 min after administration of 75 g oral glucose solution.
- ^e Plasma samples for analysis of dapagliflozin are obtained before administration of dapagliflozin at Visit 7, 10 and 12. At Visit 13 plasma samples are obtained at 60, 90, 120, 180 and 240 after administration of dapagliflozin. If the subjects perform OGTT at Visit 13, plasma samples are obtained simultaneously with OGTT blood samples.

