11.1.1 Beta-cell function and insulin resistance index

The beta-cell function and insulin resistance index will be calculated based on FPG and fasting plasma insulin using HOMA2.

The beta-cell function during an OGTT will be calculated using the insulinogenic index. The insulin sensitivity during an OGTT will be calculated using the Matsuda index or ISIcomp.

11.1.2 AUC from 0 to 180 minutes for postprandial glucose, insulin, and C-peptide response to an OGTT

The AUC from 0 to 180 minutes for postprandial glucose, insulin, and C-peptide response to an OGTT will be calculated using the trapezoidal rule.

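### The OGTT sampling schedule omits the 30-minute draw that tertiary endpoints 2(a) and 2(b) require, probably because post-dose times were labelled as post-glucose times

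*Protocol*

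**What the plan says.** Section 2.3, item 2(a), which the synopsis repeats, lists "Changes from baseline in glucose, C-peptide, and insulin concentrations at 0, 30, 60, 120 and 180 minutes during an OGTT". Item 2(b) adds the excursions from Time 0, "defined as the difference between 0 and 30, 60, 120 and 180 minute postprandial values". Both are assessed as change from baseline at Week 12, and Section 11.1 sets baseline at Week 0 before dosing.

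Section 6.3.1.2 has a Time 0 sample taken, glucose given straight afterwards, and then: "Draw blood specimens for post prandial glucose, insulin and C-peptide at 60, 90, 120, 180 and 240 minutes". That line is not limited to one visit. Two footnotes fix the origin of the clock at Week 12. Table 1 note h reads "At Visit 13, blood samples are drawn 60, 90, 120, 180 and 240 minutes after administration of 75 g oral glucose solution", and Table 8 note d (Section 7.1) says the same: "At Visit 13, blood samples are drawn 60, 90, 120, 180 and 240 min after administration of 75 g oral glucose solution".

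The PK samples carry the same five numbers on a different clock. Table 1 note i reads "At Visit 13 plasma samples are obtained at 60, 90, 120, 180 and 240 minutes after administration of dapagliflozin", and it requires PK and OGTT samples to be taken at the same moment when an OGTT is done. Under Section 6.3.1.2, at Week 12 "the study medication is given 1 hour BEFORE administration of 75 g oral glucose solution". At Week 0 the first dose follows the completed OGTT.

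Section 11.1.1 derives AUC 0-180 by the trapezoidal rule and states: "The beta-cell function during an OGTT will be calculated using the insulinogenic index". It gives no formula or time points for that index.

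**The concern.** The endpoint definitions and the sampling instructions do not describe the same test. A sample that is not drawn cannot be restored by any analysis plan, so this is an execution error and not a detail that can wait for the SAP.

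A site cannot safely work out the intended times. At Week 12 a reader might notice that the numbers make sense from the dose. At Week 0 no dose precedes the OGTT, so the glucose clock is the only one available. A site that used the dose clock at Week 12 and the glucose clock at Week 0 would have a 30-minute value with no baseline, and the change from baseline would still be lost. Its two profiles would also share only 0, 60, 120 and 180 minutes within the AUC window.

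**Working it through.** **Inputs**
- Endpoint times after glucose (Section 2.3, items 2(a) and 2(b)): 0, 30, 60, 120, 180 min.
- Draws in the procedure (Section 6.3.1.2; Table 1 note h; Table 8 note d): Time 0, then 60, 90, 120, 180, 240 min after glucose.
- Dose-to-glucose interval at Week 12 (Section 6.3.1.2): 60 min, dose first.
- PK times at Visit 13 (Table 1 note i; Section 6.6.1): 60, 90, 120, 180, 240 min after the dose.

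**1. Can the endpoint times be reproduced from the procedure?**
- Needed but not drawn: {0, 30, 60, 120, 180} minus {0, 60, 90, 120, 180, 240} = {30}.
- Drawn but not in 2(a) or 2(b): {90, 240}. The 90-minute value can enter AUC 0-180. The 240-minute value lies outside it.

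The endpoint times are not reproduced.

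**2. How much is lost?**
- 2(a): 3 analytes × 5 times = 15 measures, of which 3 × 1 = 3 are at 30 minutes.
- 2(b): 3 analytes × 4 differences = 12 measures, of which 3 × 1 = 3 use the 30-minute value.

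**3. Where do the listed times fit?** If the five times are minutes after the Week 12 dose, then post-glucose time = post-dose time − 60:

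| Post-dose (min) | 60 | 90 | 120 | 180 | 240 |
|---|---|---|---|---|---|
| Post-glucose (min) | 0 | 30 | 60 | 120 | 180 |

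The second row is exactly the endpoint grid.

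**4. Does the simultaneity rule hold as written?** Post-dose time = post-glucose time + 60. Counting Time 0, the OGTT draws fall at 60, 120, 150, 180, 240 and 300 min post-dose. PK is due at 60, 90, 120, 180 and 240.
- Shared: 60, 120, 180, 240, so four of the five PK draws have an OGTT partner.
- PK draw without a partner: 90 min post-dose. That is 30 min post-glucose, the same missing sample.

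**5. Is AUC 0-180 lost?** No. Times 0, 60, 90, 120 and 180 span the window. For illustration, assume glucose of 150, 280, 285, 260 and 190 mg/dL at 0, 60, 90, 120 and 180 min, with the 30-minute value varied:

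| Assumed 30-min value (mg/dL) | AUC, endpoint grid (mg·min/dL) | AUC, grid as written (mg·min/dL) | Difference |
|---|---|---|---|
| 200 | 42,150 | 43,050 | +900 (+2.1%) |
| 230 | 43,050 | 43,050 | 0 |
| 260 | 43,950 | 43,050 | −900 (−2.0%) |

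These glucose values are assumptions and not trial data. Insulin and C-peptide were not examined.

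**The case against.** The best case for leaving this at low priority is its reach. Only tertiary objectives are involved, and Section 12.2.1.3 reserves the ANCOVA for AUC, fasting insulin, fasting C-peptide and the HOMA2 indices. The 30-minute measures are only summarised descriptively. This stands, and it lowers the severity.

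It is also fair to say that the loss depends on sites following the text literally. Section 6.4.5 leaves detailed specimen collection to a laboratory manual that is not at hand and may carry the right times. That would still leave the protocol in conflict with the manual. The visible amendment text deals with liver monitoring and corrects nothing here.

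Some stronger readings are tempting, but the documents do not support them:
- A reader might infer that the OGTT and PK clocks cannot both be met. Once Time 0 is counted, four of five PK draws coincide with an OGTT draw, and one separate PK draw would meet both clocks. What fails is the simultaneity rule, at 90 minutes post-dose.
- A reader might infer that the insulinogenic index is lost. That follows only if it uses a 30-minute value, and Section 11.1.1 does not say so.
- A reader might take the 10 mL OGTT allowance in Table 8 as proof of a five-draw schedule. That needs an assumed 2 mL per draw. Table 8 also budgets FPG and the serum for fasting insulin and C-peptide separately, so 10 mL could equally cover five draws after Time 0.

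**Conclusion.** The inconsistency is real and appears in three places. Section 6.3.1.2, Table 1 note h and Table 8 note d do not provide the 30-minute sample that Section 2.3 needs. If sites follow the protocol as written, 3 of 15 time-point measures and 3 of 12 difference measures are lost at both visits, and a 240-minute sample is drawn that no listed OGTT endpoint uses.

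A mislabelled clock is the likely cause, because the 60-minute shift reproduces the endpoint times exactly. It remains an inference: the documents show the mismatch, not how it arose. The effect on the OGTT beta-cell index is conditional on its undefined formula. AUC 0-180 remains computable, on a different grid from the one in 2(a). The primary HbA1c analysis, both secondary endpoints and the sample size are unaffected. The point is of moderate weight, and worth acting on because the lost data cannot be recovered later.

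**What to change.** Reconcile Section 6.3.1.2, Table 1 note h and Table 8 note d with Section 2.3, and check the laboratory manual against them. State the OGTT draws as Time 0 and 30, 60, 120 and 180 minutes after the glucose load, at both Week 0 and Week 12, and name the origin of the clock each time. With the dose-to-glucose interval that the protocol already specifies for Week 12, these draws fall at 60, 90, 120, 180 and 240 minutes post-dose. The PK times then need no change and the simultaneity rule holds at all five.

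Section 11.1.1 should also say which time points the insulinogenic index uses, so that its dependence on the 30-minute value is explicit.

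The cost is a text correction to the protocol and, if needed, the laboratory manual, made before the first OGTT. Against the schedule as written, each OGTT goes from six draws over 240 minutes to five draws over 180 minutes, which is one draw and one hour less.

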6.3.1.3 Body weight and height

- The subject's weight will be recorded in kilograms (kg), to one decimal place. Measurement of weight should be performed with the subject dressed in indoor clothing, shoes removed, and bladder empty. Subjects should be weighed on the same scale at all visits.
- The subject's height will be recorded in centimetres. Measurement of height should be performed with the subject's shoes removed. The subject's knees should be straightened, head held erect, and eyes forward.

6.3.1.4 Waist

The waist should be measured in the standing position at the natural waist (smallest waist circumference). If there is no natural waist, the measurement should be made at the level of the umbilicus. Measurements should be made at the end of normal expiration.

6.4 Safety

It is of the utmost importance that all staff involved in the study is familiar with the content of this section. The investigator is responsible for ensuring this.

6.4.1 Definition of adverse events

An adverse event is the development of an undesirable medical condition or the deterioration of a pre-existing medical condition following or during exposure to a pharmaceutical product, whether or not considered causally related to the product. An undesirable medical condition can be symptoms (eg, nausea, chest pain), signs (eg, tachycardia, enlarged liver) or the abnormal results of an investigation (eg, laboratory findings, electrocardiogram). In clinical studies, an AE can include an undesirable medical condition occurring at any time, including run-in or washout periods, even if no study treatment has been administered.

For cases where it could be suspected that a tissue-derived medicine has been contaminated by a pathogen, information about any of the above conditions (including infection) should be collected.

The term AE is used to include both serious and non-serious AEs.

6.4.2 Definitions of serious adverse event

A serious adverse event is an AE occurring during any study phase (ie, run-in, treatment, washout, follow-up), that fulfils one or more of the following criteria:

- Results in death
- Is immediately life-threatening
- Requires in-patient hospitalisation or prolongation of existing hospitalisation
- Results in persistent or significant disability or incapacity
- Is a congenital abnormality or birth defect
- Is an important medical event that may jeopardise the subject or may require medical intervention to prevent one of the outcomes listed above.

For reporting purposes, all cases of cancer and overdose must be reported immediately using the SAE module of eCRF.

- Cancer
- Overdose (defined as the accidental or intentional ingestion of any dose of the investigational product that is considered both excessive and medically important)

For further guidance on the definition of a SAE, see Appendix B to the Clinical Study Protocol.

6.4.3 Recording of adverse events

Time period for collection of adverse events

All Adverse Events will be collected from the start of the Placebo lead-in Phase (Period B) throughout the treatment period including the Follow-up Phase (Period D). SAEs will be collected from the time when the informed consent is obtained until the Follow-up Phase.

Variables

The following variables will be collect for each AE;

- AE (verbatim)

- the date when the AE started and stopped
- maximum intensity
- whether the AE is serious or not
- investigator causality rating against the Investigational Product (yes or no)
- action taken with regard to investigational product
- outcome
- treatment required

In addition, the following variables will be collected for SAEs:

- Date AE met criteria for serious AE
- Date Investigator became aware of serious AE
- AE is serious due to
- Date of hospitalisation
- Date of discharge
- Probable cause of death
- Date of death
- Autopsy performed
- Causality assessment in relation to Study procedure(s)
- Causality assessment in relation to Other medication
- Description of AE

Maximum intensity will be graded according to the following definitions:

- mild (awareness of sign or symptom, but easily tolerated)
- moderate (discomfort sufficient to cause interference with normal activities)
- severe (incapacitating, with inability to perform normal activities)

- very severe (debilitating, significantly incapacitates patient despite symptomatic therapy)

It is important to distinguish between serious and severe AEs. Severity is a measure of intensity whereas seriousness is defined by the criteria in Section 6.4.2. An AE of severe intensity need not necessarily be considered serious. For example, nausea that persists for several hours may be considered severe nausea, but not an SAE. On the other hand, a stroke that results in only a limited degree of disability may be considered a mild stroke but would be an SAE.

The Investigator will assess causal relationship between Investigational Product and each Adverse Event, and answer “yes” or “no” to the question “Do you consider that there is a reasonable possibility that the event may have been caused by the investigational product?”

Causal relationship in cases where the disease under study has deteriorated due to lack of effect will be classified as no reasonable possibility.

For SAEs causal relationship will also be assessed for other medication. Note that for SAEs that could be associated with any study procedure the causal relationship is implied as “yes”.

A guide to the interpretation of the causality question is found in Appendix B to the Clinical Study Protocol.

Adverse Events based on signs and symptoms

All AEs spontaneously reported by the patient or reported in response to the open question from the study personnel: “Have you had any health problems since the previous visit?” or revealed by observation will be collected and recorded in the CRF. When collecting AEs, the recording of diagnoses is preferred (when possible) to recording a list of signs and symptoms. However, if a diagnosis is known and there are other signs or symptoms that are not generally part of the diagnosis, the diagnosis and each sign or symptom will be recorded separately.

Adverse Events based on examinations and tests

Deterioration as compared to baseline in protocol-mandated laboratory values, vital signs and other safety variables will only be reported as AEs if they are clinically significant, fulfil any of the SAE criteria, are the reason for discontinuation of treatment with the investigational product, or require the patient to receive specific corrective therapy. If a deterioration in a laboratory value/vital sign is associated with clinical signs and symptoms, the sign/symptom will be reported as an AE and the associated laboratory result/vital sign will be considered as additional information. Any new or aggravated clinically relevant abnormal medical finding at a physical examination as compared with the baseline assessment will be reported as an AE.

Clinically relevant deterioration in non-protocol-mandated measurements will be reported as AE(s).

Wherever possible the reporting investigator uses the clinical, rather than the laboratory term (eg, anaemia versus low haemoglobin value).

Hypoglycaemic events

Signs and symptoms of hypoglycaemia, hypoglycaemia episodes, or discontinuation due to hypoglycaemia should not be reported on the AE eCRF page unless the event fulfils protocol criteria for a Serious Adverse Event (see Section 6.4.2), in which case an SAE must be reported in addition to the hypoglycaemic eCRF pages for hypoglycaemia. A separate section in the eCRF will be used to document all reported episodes of hypoglycaemia.

Subjects will be given glucometers and instructed on Self Monitoring of Blood Glucose (SMBG) technique. Subjects will be recommended to monitor their finger stick glucose at regular intervals. If subjects have hypoglycemic symptoms they should measure finger stick glucose. Hypoglycaemic events (symptoms and/or finger stick glucose measurements) should be recorded into the subject's card.

The investigator is responsible for questioning the patient about all symptoms reported in the subject's card and for determining if they meet the clinical definition of hypoglycaemia. Only symptoms and/or blood glucose values deemed by the Investigator to meet the definition of hypoglycaemia should be reported on the hypoglycaemia eCRF pages (see Section 6.4.9).

Follow-up of unresolved adverse events

Any AEs that are unresolved at the end of the study or at discontinuation are followed up by the investigator for as long as medically indicated, but without further recording in the eCRF. AstraZeneca retains the right to request additional information for any subject with ongoing AE(s)/SAE(s) at the end of the study, if judged necessary.

